6.1.2 Secondary Effectiveness Endpoints

The secondary effectiveness endpoints are:

- Proportion of subjects with at least 1-point (≥ 1 -point) improvement on the MAS 'Décolleté Wrinkles – Dynamic' scale at 16 weeks after last treatment compared to baseline (Day 1). [REDACTED] A response is defined as ≥ 1 -point improvement on MAS 'Décolleté Wrinkles – Dynamic' scale at 16 weeks after treatment compared to baseline (Day 1).
- Treating investigator's treatment satisfaction assessment of aesthetic improvement in the subject after the décolleté treatments 16 weeks after last treatment.
- Subject's treatment satisfaction assessment of aesthetic improvement after the décolleté treatments 16 weeks after last treatment.
- Treating investigator's evaluation of the global aesthetic improvement on the Investigator's Global Aesthetic Improvement Scale (iGAIS) [REDACTED].
- Subject's evaluation of the global aesthetic improvement on the Subject's Global Aesthetic Improvement Scale (sGAIS) [REDACTED].

[figure not shown]

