7.1 Effectiveness Endpoints

The primary and secondary effectiveness endpoints will be summarized using the modified FAS population with missing data replaced as described in Section 7.4.1; for sensitivity purposes, these analyses will also be performed on the modified FAS with observed data and on the PPS. [REDACTED]

Statistical tests will be one-sided binomial tests at error level 2.5% for the responder rates in general. Adequate [REDACTED] statistics will be provided for each variable for the pooled data and by realized treatment group. The supportive exploratory analyses for the primary effectiveness endpoint will also be performed on the observed cases in the FAS. Metric variables will be summarized by number of observations (Nobs), number of missing values (nmiss), mean, standard deviation, median, minimum, Q1, Q3 and maximum. Categorical variables will be summarized by number and rate of events per category where the denominator will be chosen according to the adequate analysis population. Ordered categorical data may be summarized by metric and categorical statistics. All variables will be analyzed as absolute data and as change from baseline, as applicable.

Summary statistics for all visits and changes from baseline for all post-baseline visits will be displayed for each effectiveness endpoint for each treatment group and the pooled data.

If not otherwise specified, confidence intervals in the following refer to the two-sided 95% Wilson score confidence intervals.

All data captured in the electronic Case Report Form (eCRF) will be listed.

P-values will be reported to four decimal places (e.g., $p=0.0375$). P-values below 0.0001 will be presented as ' <0.0001 '.

Mean, median, and standard deviation will be reported to one decimal place more than the data were collected; for derived data, an adequate number of decimal places will be chosen. Percentages will be calculated using the denominator of all subjects in a specified population or treatment group. The denominator will be specified in a footnote to the tables for clarification if necessary. Percentages will be reported to one decimal place.

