7.1.1 Primary Effectiveness Endpoint(s)

The primary effectiveness endpoint is the proportion of responders (responder rate) defined as subjects with ≥ 1 -point improvement on the MAS 'Décolleté Wrinkles – At Rest' from baseline to 16 weeks after last treatment as assessed [REDACTED].

The primary analysis will be based on a one-sided binomial test at the one-sided type I error level of $\alpha = 0.025$ for the pooled data from both treatments against the null-hypothesis that the response rate (R) is $\leq 50\%$:

$$H_0 : R \leq 50\%$$

$$H_1 : R > 50\%.$$

H_0 is rejected if the resulting one-sided p-value is <0.025 and the observed proportion of responders is >0.5 .

As further supportive explorative analyses, the effectiveness for the different time points of treatments with a 16 weeks post-treatment period in both treatment groups will be analyzed as for the primary endpoint:

- Proportion of responders (response rate) defined as subjects with ≥ 1 -point improvement on the 'MAS Décolleté Wrinkles – At Rest' from last treatment application to 16 weeks after last treatment as assessed [REDACTED].
- Proportion of responders (response rate) defined as subjects with ≥ 1 -point improvement on the MAS 'Décolleté Wrinkles – At Rest' from last treatment application to 16 weeks after last treatment as assessed [REDACTED].
- Proportion of responders (response rate) defined as subjects with ≥ 1 -point improvement on the MAS 'Décolleté Wrinkles – At Rest' from baseline to 16 weeks after first treatment as assessed [REDACTED].

In addition, two-sided 95% Wilson score confidence intervals for response rates will be provided overall, and for each treatment group in the supportive analyses. A similar SAS code as given above will be used.

The primary effectiveness analyses will be based on the modified FAS with missing data replaced by a multiple imputation approach for each realized treatment group.

Sensitivity analyses of the primary endpoint will be provided based on observed cases only in the modified FAS and on the observed cases in the PPS. The supportive explorative analyses will be performed on the observed cases in the modified FAS as well as on observed cases in the FAS. For analysis based on observed data, SAS code similar to the following will be used:

```
proc freq data = dataset order = freq;  
  tables response / binomial (level="1" wilson p=.5) cl alpha=.05;  
run;
```

, assuming the response is coded with '1' and no response is coded with '0'.

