7.1.2 Secondary Effectiveness Endpoints

MAS ratings

One secondary effectiveness endpoint is the proportion of responders (response rate) defined as subjects with \geq 1-point improvement on the MAS 'Décolleté Wrinkles – Dynamic' from baseline to 16 weeks after last treatment as assessed [REDACTED]. Same analyses as for the primary endpoint will be performed on this endpoint (including sensitivity and supportive exploratory analyses on the same analysis sets and treatment groups).

Satisfaction with décolleté appearance

[figure not shown]
Number and percentage (n, %) of subjects with treatment satisfaction defined by a level of 1, 2 or 3 will be summarized and the corresponding two-sided 95% confidence intervals will be provided for the pooled treatment groups (overall).

[figure not shown]
GAIS

[figure not shown]
Number and percentage (n, %) of subjects with "improvement" in iGAIS-Wrinkles defined as a rating of 1, 2 or 3 at 16 weeks after last treatment will be summarized and two-sided 95% confidence intervals will be provided for the pooled treatment groups. Analogous methods will be used for sGAIS-Wrinkles.

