7.4.1 Discontinuations and Missing Data

Multiple imputation (MI)

Missing post-baseline data for the primary endpoint will be replaced by multiple imputation. Multiple imputations will only be performed for subjects with a missing MAS ‘Décolleté Wrinkles – At Rest’ score at 16 weeks after last treatment who did not discontinue before 16 weeks after last treatment due to lack of effectiveness. Subjects who will discontinue due to the reason given above will be treated as non-responders.

All further specifications for MI are based on the assumption that the MAS ‘Décolleté Wrinkles – At Rest’ assessment at 16 weeks after last treatment is missing at random, i.e.; being missing will not depend on the MAS at 16 weeks after last treatment itself but will only depend on the factors in the imputation model.

[figure not shown]

[figure not shown]
Last observation carried forward (LOCF)

For secondary effectiveness endpoints, missing values will be replaced by the last available value before 16 weeks after last treatment.

Observed cases (OC)

For the OC method, no missing value imputations will be conducted. All data will be analyzed as observed. This method will be used [REDACTED] to assess the sensitivity of the MI and the LOCF method for primary and secondary effectiveness endpoints.

7.4.2 *Interim Analyses*

Not applicable.

7.4.3 *Data Monitoring Committee*

[figure not shown]
Not applicable.

7.4.4 *Multiple Comparisons/Multiplicity*

[REDACTED] the type one error rate has not to be adjusted.

7.4.5 *Examination of Subgroups*

[figure not shown]

The supportive exploratory analyses for the primary effectiveness endpoint will also be performed for the observed cases in the FAS (i.e. on randomized treatment groups).

A further subgroup analysis for the following safety endpoints will be presented for the subgroup of subjects that had three injections with a cannula:

- Adverse events: Incidences of TEAEs, non-serious TEAEs and serious TEAEs will be provided by SOC and PT. Incidences of TEAEs will be provided overall and by worst intensity, by worst outcome, and by treatment area affected (yes/no). Treatment-related TEAEs will be presented by injection cycle.

[figure not shown]

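### The SAP is ambiguous on whether missing MAS-Dynamic responses follow the primary's multiple imputation and non-responder rule or plain LOCF

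*SAP*

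**What the plan says.** SAP 6.1.2 opens its list with "The secondary effectiveness endpoints are", and MAS-Dynamic response is the first item. SAP 7.1 refers both primary and secondary endpoints to 7.4.1 for missing data.

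SAP 7.4.1 then treats the two classes differently:

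- **Primary, At Rest.** "Multiple imputations will only be performed for subjects with a missing MAS" At Rest score at the 16-week time point, provided they did not discontinue earlier for lack of effectiveness. For those who did: "Subjects who will discontinue due to the reason given above will be treated as non-responders".
- **Secondary.** "For secondary effectiveness endpoints, missing values will be replaced by the last available value before 16 weeks after last treatment". The visible text makes no exception by reason for discontinuation.

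For MAS-Dynamic, SAP 7.1.2 says: "Same analyses as for the primary endpoint will be performed on this endpoint (including sensitivity and supportive exploratory analyses on the same analysis sets". The rest of that sentence extends this to the groups analysed. The primary analysis it points to is defined in SAP 7.1.1 as the modified FAS with "missing data replaced by a multiple imputation approach for each realized treatment group".

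Two further rules decide who is filled and with what. Under SAP 7, a subject with no visit 12 to 20 weeks after the last treatment is missing at this time point, even if still in the study. Under SAP 3.1, assessments at injection visits were made before the injection.

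**The concern.** A programmer can follow 7.1.2 and run MI with the non-responder rule on Dynamic, or follow 7.4.1 and run LOCF. The two can give different rates.

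The LOCF route has two weaknesses. First, both MAS endpoints are improvements of at least 1 point from baseline at the same time point, and for At Rest the SAP treats leaving for lack of effectiveness as failure. Under LOCF the same departure can count as success on Dynamic if the last Dynamic score happened to be improved. Second, the last available score may have been taken before the last injection, yet it would represent the effect 16 weeks after that injection. If the baseline score is the one carried, the change is zero and the subject is a non-responder, which is conservative. Otherwise the direction is uncertain.

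At stake is whether two response rates that readers will compare directly rest on the same treatment of missing subjects.

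**Working it through.** **Inputs.** From Protocol 12.1: 112 enrolled, allowance of up to 10% for drop-outs and FAS exclusions, at least 100 remaining. From SAP 7.1.1: one-sided binomial test of a response rate of 50% or less, at 0.025, on the pooled groups. SAP 7.1.2 carries this test over to MAS-Dynamic.

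**The plan's own figure.** 100/(1 − 0.10) = 111.1, rounded up to 112. This reproduces. The stated 90% power cannot be checked because no assumed response rate is visible, but it is not needed here.

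**Assumptions.** All 112 subjects are in the modified FAS and every missing Dynamic value is filled. Let k be the number of subjects who discontinue for lack of effectiveness, are missing at 16 weeks after the last treatment, and carry a Dynamic improvement of at least 1 point. The documents do not give k.

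**Effect on the rate.** LOCF counts these k subjects as responders; the primary's rule would not. With everything else held fixed, the difference is k/112:

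| k | Difference (percentage points) |
|---|---|
| 1 | 0.9 |
| 2 | 1.8 |
| 3 | 2.7 |
| 6 | 5.4 |
| 11 | 9.8 |

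The last row is an outer limit. It takes roughly the whole 10% allowance (0.10 × 112 = 11.2) to be subjects of this kind.

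**Effect on the test.** Exact one-sided tail probabilities for X ~ Binomial(112, 0.5):

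| Responders | P(X ≥ count) |
|---|---|
| 66 | 0.0361 |
| 67 | 0.0234 |
| 68 | 0.0147 |
| 69 | 0.0089 |
| 70 | 0.0052 |

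The smallest significant count is therefore 67 of 112. The large-sample test has the same cut-off (p = 0.0188 at 67 and 0.0294 at 66), so this does not depend on which version is run.

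Taking k responders away turns a significant LOCF result into a non-significant one only if the LOCF count lies from 67 to 66 + k. With k of 3 or fewer, that is 67 to 69 of 112 (59.8% to 61.6%). For example, 67 under LOCF with k = 1 becomes 66 (p = 0.0361), so significance is lost. But 70 under LOCF with k = 3 becomes 67 (p = 0.0234), so the result stands.

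**What is not sized.** The full difference between LOCF and MI also depends on how often carried scores are responses and on the imputation model. Neither is visible, so no figure is given.

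**The case against.** **The passages can be reconciled.** Section 7.4.1 assigns methods by endpoint class, and its observed-case paragraph repeats the split, saying that method serves "to assess the sensitivity of the MI and the LOCF method for primary and secondary effectiveness endpoints". The parenthesis in 7.1.2 names sensitivity and supportive analyses, sets and groups, but not imputation. On that reading, Dynamic gets the primary's test, intervals and sets, with missing data by LOCF. This stands to the extent that a reader who infers a flat contradiction goes too far. But 7.1.1 defines the primary analysis with MI, so the other reading is also fair. Reconciling the texts also leaves the missing non-responder rule untouched.

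**Hidden text may supply the rule.** Material directly before the LOCF heading is not shown, so an additional rule cannot be excluded. The visible LOCF sentence is complete, however, and has no exception. A reader might also infer the same gap in the protocol, since the visible sentence of Protocol 12.4.4.1 covers only the primary. That text breaks off and may be redacted, so it does not support the inference.

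**Few subjects may differ.** LOCF carries a score, not a response. Someone who leaves for lack of effectiveness may well have an unimproved last Dynamic score and be a non-responder either way. At Rest and Dynamic are also separate scales, so opposite results are not in themselves inconsistent. Both points stand and keep the likely effect small. What remains is that one result would be set by rule and the other by a carried score, with no visible reason for the difference.

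**Sensitivity analyses are planned.** SAP 7.1 says that "for sensitivity purposes, these analyses will also be performed on the modified FAS with observed data and on the PPS". These will show part of the dependence on LOCF. They impute nothing, so they leave out the subjects concerned and do not count them as failures.

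**Conclusion.** The point holds as an ambiguity about which missing-data method applies to MAS-Dynamic, together with a weak rule if LOCF is the one followed. Each affected subject moves the pooled Dynamic rate by 0.9 points. With up to three, the test result changes only in the narrow band of 67 to 69 responders of 112. This rests on 112 filled values and on an unknown number of affected subjects.

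It is minor. MAS-Dynamic is secondary, no visible text gives it a confirmatory role, and the primary analysis has its own rule and is unaffected.

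A reader might extend the criticism to the GAIS-Wrinkles and satisfaction rates, which also fall under LOCF. The documents do not support that step on the same ground: SAP 7.1.2 gives those endpoints counts, percentages and confidence intervals, and nowhere gives them the primary's analysis.

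**What to change.** State in SAP 7.1.2 and 7.4.1 that the main MAS-Dynamic analysis uses the primary's MI approach, with Dynamic scores in place of At Rest scores, and the same rule that discontinuation for lack of effectiveness before the 16-week time point is non-response. Keep LOCF for MAS-Dynamic as a labelled sensitivity analysis. If text not shown already applies that non-responder rule to Dynamic, the wording on the imputation method still needs aligning.

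The cost is SAP wording and a little programming to run the existing approach on a second score. The Dynamic rate may come out slightly less favourable, or its interval slightly wider. No new data are needed.

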Statistical tests will be one-sided binomial tests at error level 2.5% for the response rates in general. Statistics will be provided for each endpoint for the pooled data and by realized treatment group. The supportive exploratory analyses for the primary effectiveness endpoint will also be performed on the observed cases in the FAS. Metric variables will be summarized by number of observations, mean, standard deviation, min. median and max. Categorical variables will be summarized by number and rate of events per category where the denominator will be chosen according to the adequate analysis population. Ordered categorical data will be summarized by metric and categorical statistics. All variables will be analyzed as absolute data and as change from baseline, as applicable.

If not otherwise specified confidence intervals in the following refer to two-sided 95% Wilson score confidence intervals.

All data captured in the electronic CRF will be listed.

Primary Effectiveness Endpoint

The primary effectiveness endpoint is the proportion of responders (response rate) defined as subjects with \geq 1-point improvement on the MAS Décolleté Wrinkles-At Rest from baseline to 16 weeks after last treatment as assessed.

The primary analysis will be based on a one-sided binomial test at the one-sided type I error level of $\alpha = 0.025$ for the pooled data from both treatment groups to test the null-hypothesis that the response rate is $\leq 50\%$ versus the alternative that response rate is $\geq 50\%$:

As further supportive explorative analyses, the effectiveness for the different time points of treatments with a 16 weeks post-treatment period in both treatment groups will be analyzed on the observed cases in the modified FAS as for the primary endpoint:

- Proportion of responders (response rate) defined as subjects with ≥ 1-point improvement on the MAS Décolleté Wrinkles-At Rest from last treatment application to 16 weeks after last treatment as assessed in treatment group A.
- Proportion of responders (response rate) defined as subjects with ≥ 1-point improvement on the MAS Décolleté Wrinkles-At Rest from last treatment application to 16 weeks after last treatment as assessed treatment group B.
- Proportion of responders (response rate) defined as subjects with ≥ 1-point improvement on the MAS Décolleté Wrinkles-At Rest from baseline to 16 weeks after first treatment as assessed in treatment group B.

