7.4 Removal of Subjects from Treatment or Assessment

7.4.1 Discontinuation of Subjects

In accordance with the Declaration of Helsinki and the informed consent form, the subject may discontinue the investigation at any time without any penalty or loss of benefits to which the subject is otherwise entitled (see Section 7.4.3). Premature discontinuation of the investigation with its reason(s) must be recorded in the subject file and the eCRF. Date and discontinuation circumstances should be stated.

Subjects must be discontinued from the investigation by the investigator at any time for any of the following reasons:

• Withdrawal of informed consent.

- Pregnancy (no further injection of IMD, or any other interventional procedure will be performed).
- Any AEs for which treatment continuation would constitute an unacceptably high risk for the subject.

CIP deviations or conditions arising from the exclusion criteria established in Section 7.3, may lead to the subject's discontinuation. All such conditions should be properly documented.

Subjects who are discontinued from the investigation due to AEs will be treated according to standard clinical strategies and will be followed-up until the final investigational visit/safety visit. All pertinent information concerning the AE will be documented in the subject file as well as in the eCRF AE report form.

Following discontinuation, a final examination should be performed for safety reasons. The investigator is required to make every effort to contact subjects lost to follow-up, and all such efforts should be documented in the subject file (e.g., times and dates of telephone contact, copies of letters).

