10.1.2 Adverse Event Handling and Reporting

Data pertaining to AEs will be collected during the telephone contact 24 or at latest 48 hours after each IMD treatment and during each clinical investigation visit based on the subject's spontaneous description, through investigator inquiry, or discovered in the course of examinations done during the visit.

At each clinical investigation visit, the investigator will assess and record any AE in detail in the source data and on the eCRF AE report form. The following information must be recorded:

- AE diagnosis or main symptom;
- Location of AE: outside of injection area, (e.g. systemic) or restricted to injection area. In case of local reaction, the corresponding area should be reported;
- Date of onset;
- Date of worsening;
- Severity (maximum observed; see Section 10.1.3);
- Causal relationship (not related, related);
- Serious (yes or no), date serious since and reason for seriousness;
- Outcome (see Section 10.1.5);
- AE leading to discontinuation of the clinical investigation (yes or no);
- Stop date.

If on-site visits are not possible due to COVID-19 pandemic and the subject provides his/her consent to safety assessments on the phone, safety assessments (AEs, change in medication and non-drug treatment, and occurrence of pregnancy) will be performed via phone calls and the results documented in the source data first and in the eCRF subsequently. For documentation requirements, please refer to section 11.2.

For all adverse events that are collected during telephone visits, it is up to the medical judgement of the investigator to refer a subject to a specialist if deemed necessary, thus ensuring the safety of the subject and the accuracy of the data.

For documentation of a COVID-19 positive test result see Section 10.1.1.

After completion of all scheduled visit assessments the investigator must document any AEs arising from these assessments.

In case of an SAE (defined in section 10.2), the investigator must also complete an SAE report form and report it to Merz and the CRO immediately, as described in Section 10.2.2.

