5 ANALYSIS SETS

The following analysis sets are defined for the statistical analysis of this clinical study:

Safety Evaluation Set (SES)

The SES is the subset of all randomized subjects who were exposed to the IMD at least once. Subjects will be analyzed as treated.

[figure not shown]

Full Analysis Set (FAS)

The FAS is the subset of subjects in the SES for whom at least the baseline value of the primary effectiveness variable is available (i.e., all subjects who have a baseline value on the MAS Décolleté Wrinkles – At Rest scale). In contrast to the SES, subjects will be analyzed as randomized.

Modified Full Analysis Set

The modified FAS is the subset of the subjects in the SES for whom at least the baseline value of the primary effectiveness variable is available (i.e., all subjects who have a baseline value on the MAS Décolleté Wrinkles – At Rest scale). Subjects will be analyzed as treated.

Per Protocol Set (PPS)

The PPS is the subset of subjects in the modified FAS without major protocol deviations. Subjects of treatment group A switching to treatment group B will not be excluded from the PPS per se, as this is in line with protocol amendment 4. Further major protocol deviations and other reasons leading to exclusion will be defined prior to database lock during a data review meeting (DRM).

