7.2 Safety Endpoints

All safety analyses will be performed on the SES.

AEs will be coded according to the Medical Dictionary for Regulatory Activities (MedDRA) version in effect at the time the database is closed. Only TEAEs will be analyzed, which are defined as AEs with onset or worsening at or after date of first injection of the IMD. Incidences will be calculated for TEAEs on the system organ class (SOC) level and on the preferred term (PT) level (i.e., total and percentage, by intensity, and by relationship). Listings and (as

applicable) tables displaying incidences for TEAEs leading to discontinuation, serious TEAEs, and deaths will also be provided.

Each documented worsening of an AE will be aggregated with the previous corresponding AE record. The start date of the AE will be the date of the record reporting the onset of the AE with the first reported intensity and the stop date will be the last stop date of all aggregated worsening records or considered ongoing, if not yet resolved. For intensity, the worst attribute will be chosen.

CAVE: there is one exception, where an aggregation of the AE with corresponding worsening(s) is not allowed: if the AE record started before the first treatment and the worsening record started (worsened) at or after date of first treatment. In that case, only the AE record(s) starting at or after treatment will be aggregated and regarded as TEAE (see also below).

[figure not shown]
In case of missing intensity or missing causal relationship of an AE the worst case principle will be applied, i.e. a missing intensity will be set to “severe” and a missing causal relationship will be set to “related”. Missing data of the worst outcome will be imputed by “unknown”.

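### Does limiting the cannula safety subgroup to subjects with three injections hide adverse events that ended treatment early?

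*SAP*

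**What the plan says.** SAP 7.4.5 (Examination of Subgroups): "A further subgroup analysis for the following safety endpoints will be presented for the subgroup of subjects that had three injections with a cannula". The outputs are TEAEs, non-serious TEAEs and serious TEAEs by SOC and PT, with breakdowns by worst intensity, worst outcome and whether the treatment area was affected. In addition, "Treatment-related TEAEs will be presented by injection cycle".

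Protocol 7.4.1 (Discontinuation of Subjects) lists among the mandatory reasons for stopping: "Any AEs for which treatment continuation would constitute an unacceptably high risk for the subject". It also says: "Premature discontinuation of the investigation with its reason(s) must be recorded in the subject file and the eCRF".

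Protocol 6.2 gives two regimens, of two or three injection cycles. SAP 7 explains that group A subjects who skipped the second injection because of COVID-19 measures count in realized group B. Group A is therefore inferred to be the three-injection group.

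For the main safety analysis, SAP 5 states: "The SES is the subset of all randomized subjects who were exposed to the IMD at least once". SAP 7.2 places all safety analyses on that set and adds listings and, as applicable, "tables displaying incidences for TEAEs leading to discontinuation, serious TEAEs, and deaths will also be provided". The Protocol synopsis says in general terms: "Statistics will be provided for each endpoint for the pooled data and by realized treatment group".

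**The concern.** The subgroup is formed by something that happens after baseline and that the safety outcome can itself determine. An adverse event serious enough to end treatment before the third injection removes the subject from the table in which a reader might look for it. The by-cycle presentation is the clearest case: its rows for cycles 1 and 2 contain only subjects who went on to injection 3, so a related event that ended treatment after cycle 1 is absent from the cycle 1 row.

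In the readable text this is the only output restricted to three cannula injections and the only one split by cycle. Someone who took it as the adverse event profile of everyone who started that regimen by cannula would see too favourable a picture of the events that led to stopping.

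**Working it through.** **The plan's own safety figures.** SAP 4 and Protocol 12.1 claim an 80% chance of seeing at least one event of true probability 1.6% among 100 subjects. Check: 1 − (1 − 0.016)^100 = 0.8007, which agrees. Enrolment: 100 / (1 − 0.10) = 111.1, rounded up to 112, or 56 per group (Protocol 12.1). These figures concern the safety evaluation set; none is given for the cannula subgroup.

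**Inputs for the size of the effect.**
- N: subjects who started the three-injection regimen and were treated by cannula throughout. Not given. The upper bound is 56 (all of planned group A); 28 is an assumption (half treated by cannula).
- k: those stopped for an adverse event before injection 3. Not given. For a ceiling, the whole 10% allowance for drop-outs and FAS exclusions is assigned to such stops: 10% of 56 = 5.6, so at most 5. This is not an estimate.
- p: TEAE incidence among subjects with three injections. Not given; 50% is an assumption.

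**Overall TEAE incidence.** If every stopped subject has a TEAE, incidence among all N is [p(N − k) + k]/N. The subgroup figure is lower by (k/N)(1 − p), which is at most k/N.

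| N | k | Maximum shift k/N | Shift at p = 50% |
|---|---|---|---|
| 56 | 0 | 0 | 0 |
| 56 | 1 | 1/56 = 1.8 points | 0.9 points |
| 56 | 5 | 5/56 = 8.9 points | 4.5 points |
| 28 | 1 | 1/28 = 3.6 points | 1.8 points |

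**Single SOC or PT terms.** Let q be the incidence of a term in the subgroup and r its incidence among the stopped subjects. Subgroup minus all starters = (k/N)(q − r). The sign depends on which is larger. With N = 56, k = 5 and 51 completers:
- Term only in the stopped subjects: 0/51 = 0% against 5/56 = 8.9%.
- Term in 5 completers and all 5 stopped: 5/51 = 9.8% against 10/56 = 17.9%.
- Term in 5 completers and none stopped: 5/51 = 9.8% against 5/56 = 8.9%, so here the subgroup figure is higher.

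Under-statement is therefore certain only for the events that caused the stop.

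**Where the stopped subjects appear.** They had at least one injection, so they are in the safety evaluation set and in every pooled safety table. Their events enter the discontinuation outputs of SAP 7.2. Protocol 10.1.2 records for each adverse event whether it led to discontinuation, Protocol 7.4.1 keeps subjects discontinued for adverse events under follow-up, and SAP 7.1 has all eCRF data listed.

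**Would a companion table be cleaner?** The natural candidate is everyone on the regimen with at least one injection, all by cannula. That set is also defined after baseline, and it asks one cannula use of a subject stopped after injection 1 but three of a completer. If the instrument can vary between injections (the rules are not readable), take an assumed independent probability of 0.5 per injection: 0.5 of one-injection stoppers qualify, against 0.5^3 = 0.125 of completers. Early stoppers would then be over-represented four to one.

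**The case for a change.** The strongest case for a change is that it would be cheap and would prevent a misreading. Treatment dates, the discontinuation flag and the reason for stopping are all collected, so a label, a count of early stops and a companion table need only programming. The main safety tables do not fully substitute for this one: in the readable text they show neither the cannula restriction nor the cycle split. An event seen only in early stoppers shows as 0% here, however many of them there are.

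The factual part of this stands. The inference to a change does not. A table titled by the subgroup's definition already tells the reader that it covers three received cannula injections. Describing events at full exposure is a legitimate question, and a fixed set of subjects lets the three cycles be compared without drop-out changing the denominator. The alleged gap also cannot be established: material around the subgroup paragraph in SAP 7.4.5 and in 7.2.2 is not shown, and 7.3 is absent from the readable text, so a companion output may already exist. The table that would be added has a selection problem of its own.

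**Conclusion.** No change to the plan is needed. The subgroup does exclude subjects stopped before the third injection, and its incidences are conditional on reaching it. They are nevertheless correct for the population named, are descriptive only, and sit beside safety analyses that keep every injected subject and report events leading to discontinuation. The trial's safety conclusion does not depend on this output.

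The size is unknown, because the number of stops, the cannula share and the completer incidence are not in the documents. Under the stated assumptions one stop moves the overall TEAE incidence by at most 1.8 points (N = 56) or 3.6 points (N = 28). The 8.9-point ceiling needs all five allowed losses among 56 subjects to be adverse event stops, and with none the effect is zero. For individual terms the direction is not fixed.

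Whoever writes the tables may footnote how many subjects on the three-injection regimen stopped before injection 3 for an adverse event and, separately, for other reasons. That is an optional courtesy to the reader which the collected data already support.
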